### **Study Design and Methodology**

After informed consent has been obtained, all study participants will receive spinal anesthetics based on their height to provide anesthesia for their cesarean sections as per our usual clinical practice. Patients  $\geq 64$  inches will get spinal anesthetics containing 12mg 0.75% bupivacaine (1.6ml), 10mcg fentanyl (0.2ml), and 200mcg PFM (0.4ml) for a total volume of 2.2ml. Patients  $\leq 63$  inches will receive the same spinal anesthetic as those  $\geq 64$  inches except that the dose of 0.75% bupivacaine be reduced to 10.5mg (1.4ml) resulting in a total volume of 2.0ml. The PFM dose of 200mcg was chosen as it is the commonly used clinical dose (28). These spinal anesthetics reliably provide anesthesia for 1.5-2hr in each patient population. The patients will have been randomly assigned to one of three study arms prior to initiation of the anesthetic using a computer generated random number list. The randomization list has already been created using a randomization free-ware packet from the internet (Random Number Generator,

stattrek.com), and is on file at the research pharmacy. The code is not known by any of the investigators. The arms are as follows: 1) a bolus dose of 8ml of normal saline followed by an infusion of 8ml/hr of normal saline using an On-Q® elastomeric pump, 2) a bolus dose of 8ml of 0.1% ropivacaine followed by an infusion of 8ml/hr of 0.1% ropivacaine using an On-Q® elastomeric pump, or 3) a bolus dose of 8ml of 0.2% ropivacaine followed by an infusion 8 ml/hr of 0.2% ropivacaine using an  $On-Q^{\mathbb{R}}$ elastomeric pump. The pump will be filled to its maximum capacity of 550 ml and will infuse until the total volume is delivered. The patients will undergo their cesarean sections in the usual fashion through uterine closure. The peritoneum may or may not be closed and the rectus abdominis muscles may or may not be approximated as per the usual practice of the attending obstetrician. The obstetrician will insert a 20G guide needle/introducer assembly through the skin, subcutaneous tissue and rectus fascia about 3cm above and just lateral to the incision. When the introducer is fixed in the desired location, the guide needle is removed, and a multiport, silver-impregnated catheter (6-10cm) is placed above the rectus muscle parallel to the fascial incision. The fascia is then closed above the rectus muscles, and the rest of the closure occurs as per the usual practice of the surgeon. After closure is complete, one to two drops of a topical skin adhesive (2-octvl cvanoacrylate or SurgiSeal®) will be placed on the skin at the exit site of the multiport catheter and the catheter will be further secured with adhesive surgical strips. The exit site, along with a small length of catheter will then be covered with a sterile bio-occlusive dressing. The hospital pharmacy will have delivered a 10 ml syringe filled to 8ml with the bolus test solution, along with an On-Q® elastomeric pump loaded with the same solution to the operating room prior to, or during, the cesarean section. The test solutions are all water-white in color, and will have no discerning markings to indicate whether it is saline or one of the two concentrations of ropivacaine. The preparing pharmacist will be the only person not blinded to the study. At the termination of the surgical procedure, the obstetrician will administer the 8ml bolus of test solution via the catheter using the 10ml preloaded syringe, followed by attaching and activating the elastomeric pump which will be pre-set to deliver 8ml/hr of test solution.

Ketorolac (30 mg IV) will always be given at the first request for additional pain medicine after leaving the operating room. Thereafter, the study patients will receive 30mg ketorolac q6hr prn pain for 24hr if their pain score is > 3. If their pain score remains > 3 twenty minutes after ketorolac administration, they can receive morphine 1mg IV q1hr until their pain score is  $\leq$  3. After 24hr, and through discharge, the study patients will receive1-2 tablets PO oxycodone-acetaminophen (5/325) q6hr for postoperative pain for pain scores > 3. Additional breakthrough pain still present 30 min after oxycodone-acetaminophen dosing will be treated with ibuprofen 600 mg PO q6hr. Again, if the pain score remains > 3 thirty min after ibuprofen dosing, IV morphine (1-2 mg q1hr) will be administered until the pain score is  $\leq$  3.

Each patient that ends up participating in our study will have a folder (see attached Data Collection Instrument) associated with her name. This folder will include all of the VAPS scoring sheets and the McGill pain scoring sheets obtained at the different time periods. It will also contain summary sheets for data abstracted from the medical, nursing, and pharmacy records such as uterine closure, LATCH scores, time to first rescue medication, time to first opioid use, and total opioid and NSAID use, etc. These folders will be stored in locked file cabinets in the main office of the EUHM Department of Anesthesiology where other sensitive patient information is kept securely. Data, without personal identifiers will be entered into Excel spread sheets and kept on the Emory Healthcare virtual desktop for further analysis.

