### **IRB** Protocol

### Multimodal Post-Cesarean Analgesia with Spinal Morphine and Continuous Wound Infiltration of Ropivacaine Using the OnQ® Elastomeric Pump: A Dose-Ranging Study Using a High-Volume, Low-Dose Protocol PI: [name]

Abstract:

The purpose of the proposed study is aimed to determine whether continuous subfascial infusion of ropivacaine using the On-O® elastomeric pump in combination with intrathecal (IT) preservative-free morphine (PFM) will improve post-operative cesarean section pain relative to IT PFM alone (the current standard of care). Using a doubleblinded, randomized, placebo-controlled study design, 60 women undergoing their first, second or third cesarean section will be randomly assigned to one of 3 different groups receiving either saline (control, n=20) or ropivacaine (0.1% or 0.2%, experimental groups n=20 in each) subfascially via the elastomeric pump. We will enroll up to 70 subjects to achieve 60 randomized and treated subjects, to account for screen failures and/or early terminations, All participants will receive an IT dose of 200mcg of PFM as part of a standardized spinal anesthetic for their operative procedure. During closure of their abdomen, all patients will undergo placement of a multi-orifice, silver-impregnated catheter in the subfascial space. At the conclusion of the surgery, the catheter will be bolused with 8ml of one of the three test solutions, after which an On-O® elastomeric pump (containing the same solution as initially administered through the catheter) will be attached to infuse the test solution at a rate of 8ml/hr. The infusion system will then be left in place for up to 72hr. Adjunctive pain medicines (ketorolac, morphine, ibuprofen, and oxycodone-acetaminophen) will be available for the treatment of breakthrough pain during hospitalization. The primary outcome being measured in the study is postoperative pain with movement as assessed immediately after the study bolus (baseline) and during the immediate post-operative period, when leaving the PACU (2hr), 6hr, 12hr, 24hr, 48hr, and 72hr post-op. Pain will also be evaluated by telephone at 4-6 weeks and 3mo after surgery. A visual acuity pain scale (VAPS) will be used to measure patient pain levels while hospitalized whereas pain at the 4-6 week visit and 3mo will be quantitated using a numeric pain scale (NPS). Secondary outcomes to be studied include degree of pain at rest, time to first rescue medication, time to first opioid use, amount of

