# **Objectives:**

The primary outcome measured in this study is post-operative pain with movement measured both during cough and 20° straight leg raise. Pain at rest will also be evaluated. All types of pain will be measured using a visual analogue pain scale (VAPS) determined using a 100mm line with the patient making a mark on the line between no pain and worst pain ever (12). Pain scores will be collected after the bolus of study medication/placebo (zero time), at PACU discharge (2hr), 6hr, 12hr, 24hr, 48hr, and 72hr post-cesarean section. Pain at 4-6 weeks and 3mo will be quantitated over the telephone using a numerical pain scale (NPS) with 0 being no pain and 10 being the worst pain imaginable. In addition to the pain scores, pain with movement will be further evaluated qualitatively using the short-form McGill pain questionnaire (22) at all time-points in the study. This will allow us to look at pain quality (sharp, burning, etc.), as well as examining the affective components (exhausting, fearful, etc.) of the pain.

There are several secondary outcomes of this study that can be divided into rescue medication information, medication side effects, breastfeeding, wound evaluation, patient satisfaction, and cost-analysis.

Rescue medication data will be collected during the hospitalization period (0-72hr). We will note the time to dosing with the first rescue medication for breakthrough pain. After the first rescue medication is given, the patients will be eligible for further doses of IV or

PO pain medicines for continued breakthrough pain as needed (see **Study Design and Methods** section below for specifics). The time to first opioid use for pain will also be recorded whether this entails IV or PO administration. Additionally, we will quantitate narcotic use in terms of morphine equivalents given (in mg) both by post-operative day and with a cumulative total. The total dose of NSAIDs (in mg) will be recorded for each of the first three postoperative days, along with a cumulative total. We will also be measuring the proportion of patients who require opioid supplementation at 0, 2, 6, 12, 24, 48, and 72 hours post-op. We will also ask if patients are still requiring opioids and/or NSAIDs for surgical discomfort along with inquiring about the amount of each used per day at the 4-6 week and 3 month follow-up telephone calls.

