# **Statistical Analysis**

Based on a preliminary sample size calculation using an  $\alpha$  risk of 0.05, a  $\beta$  risk of 0.2, and an effect size involving a 40% reduction in pain scores, we estimate that 20 patients are needed in each arm of the study. Data normality will be tested using the Kolmorgorov-Smirnov test. Normally distributed data will be presented as means  $\pm$  SD, whereas non-normally distributed data will be expressed as medians with interquartile ranges. Categorical data will be reported as frequencies. VAS scores will be analyzed using two-way ANOVA for repeated measures. Non-normal data will be analyzed using the Friedman test. Categorical data will be analyzed using the X test. Multiple comparisons will use a Bonferroni correction. Differences will be considered statistically significant at a P<0.05.

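### All arms share a rescue ladder aimed at a pain score of 3 or below, but the movement-pain analysis ignores rescue, so a real benefit would be attenuated and no planned analysis reads pain and rescue together

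*Combined protocol and SAP*

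**What the plan says.** Under Objectives, "The primary outcome measured in this study is post-operative pain with movement measured both during cough and 20° straight leg raise". Scores are taken on a 100 mm line at zero time, 2, 6, 12, 24, 48 and 72 hours.

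Under Study Design and Methodology, all arms share one rescue scheme. Ketorolac is given at the first request and then as needed. If the score is still above 3 twenty minutes later, "they can receive morphine 1mg IV q1hr until their pain score is" 3 or below. After 24 hours the sequence is oxycodone-acetaminophen, ibuprofen and then IV morphine to the same target. The text speaks only of a pain score; it does not say whether this is at rest or with movement.

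Under Statistical Analysis, "VAS scores will be analyzed using two-way ANOVA for repeated measures", with the Friedman test for non-normal data. Rescue is not mentioned there. The sample size uses a beta "risk of 0.2, and an effect size involving a 40% reduction in pain scores", and "we estimate that 20 patients are needed in each arm of the study". No control mean, SD or rescue allowance is given.

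Time to first rescue, time to first opioid, morphine equivalents, NSAID milligrams and the proportion needing opioid are listed under Objectives as secondary outcomes. Nothing in the text supplied times a pain score relative to a rescue dose, or combines pain with rescue.

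**The concern.** Rescue depends on the score, and the score is the outcome. A saline woman brought down from 7 to 3 shortly before the 12-hour assessment counts the same as a ropivacaine woman who is at 3 without rescue. The protocol itself expects unequal rescue: the Introduction and the section on safety and benefits both anticipate less opioid use with ropivacaine. The Introduction also reports that more than 70% of women given neuraxial opioids ask for further analgesia. Part of a true benefit would therefore move out of the primary outcome and into rescue consumption.

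The protocol's own background shows the pattern. It cites a subcutaneous infusion trial with no difference in rest pain but 22 mg less morphine over 24 hours, as an example of disappointing results. If this trial produced the same pattern, the plan has no rule for reading it. An interpretation built afterwards from one of many secondary outcomes would be post hoc.

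**Working it through.** **Step 1. The plan's own figure.** The 20 per arm cannot be verified, because no mean or SD is stated. Working backwards, a two-sided 0.05 t-test with 20 per arm and 80% power needs a standardised difference of 0.909. With a 40% reduction, SD / control mean = 0.40 / 0.909 = 0.44. If the control mean is 50 mm (assumed), the difference is 20 mm and the SD is 0.44 × 50 = 22 mm. Check: 2 × (1.960 + 0.842)² × (22/20)² = 2 × 7.85 × 1.21 = 19.0 per arm by the normal formula, and 20 by the t-test. The result depends heavily on the ratio: by the normal formula, ratios of 0.3 and 0.8 give 9 and 63 per arm.

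**Step 2. Model for rescue (all assumed).** Movement scores are normal with mean 50 mm (saline) or 30 mm (ropivacaine) and SD 22 mm, cut to 0–100. A score of 3 is read as 30 mm. A fraction f of triggered women has been rescued by scoring time.
- Movement trigger: women above 30 mm are triggered; rescue resets movement pain to 15–30 mm (uniform).
- Rest trigger: rest pain is taken as half of movement pain, so women above 60 mm on movement are triggered; rescue resets rest pain to 15–30 mm and movement pain to 30–60 mm.

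Before cutting, the movement trigger catches P(Z > (30 − 50)/22) = 82% of saline women and 50% of ropivacaine women. At f = 0.5 that is 41% versus 25% rescued. The rest trigger catches 32% and 9%, so 16% versus 4% are rescued.

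**Step 3. Result at one time point, 20 versus 20, two-sided t-test (simulated).**

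| Trigger | f | Difference (mm) | Power |
|---|---|---|---|
| none | 0 | 19.1 | 79% |
| movement | 0.25 | 15.2 | 61–62% |
| movement | 0.50 | 11.3 | 44–45% |
| movement | 0.75 | 7.3 | 30–31% |
| rest | 0.50 | 15.5 | 72% |
| rest | 0.75 | 13.7 | 69% |

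Ranges are the spread between repeat simulations. The first difference is 19.1 rather than 20 because scores are cut at 0 and 100.

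**Step 4. Other control means, movement trigger, f = 0.5.** With SD held at 22 mm, power goes from 61% to 39% at a control mean of 40 mm, and from 92% to 45% at 60 mm. If the SD is instead scaled with the mean (0.44 × 40 = 17.6 mm; 0.44 × 60 = 26.4 mm) so that power without rescue stays near 80%, the results are about 52% and 38%.

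**Step 5. Extreme case.** Suppose every woman above 30 mm on movement is rescued to exactly 30 mm, with the SD at 0.4515 of the control mean (the normal-formula ratio for 20 per arm). Then 65%, 31% and 20% of the difference survives at control means of 30, 50 and 70 mm, with power of 74%, 56% and 45%. The difference does not vanish, because scores below 30 mm are untouched and still differ by arm. Power falls less than the difference does, because rescue also narrows the spread.

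**The case against.** A reader might infer that rescue removes the difference and that a null result would inevitably be misread. The documents do not support either. Even the extreme case in Step 5 keeps part of the difference, and the rescue outcomes are named and collected, so a shift of benefit into lower drug use would be visible.

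Further points count against a large effect:
- The trigger may be rest pain, in which case the loss is modest. The Introduction describes movement pain as often above 3/10 despite neuraxial opioid and NSAID, which leaves room for a difference.
- Rescue in the first 24 hours is on request or as needed, and morphine is permitted rather than mandated. The fraction rescued is unknown.
- "an effect size involving a 40% reduction in pain scores" has no stated source. The ladder is described as usual care, so the 40% may already be a difference seen with rescue available. The calculation above would then count rescue twice.
- The planned analysis uses seven times, not one, and the zero-time score precedes ward rescue.
- Pain scores under usual rescue answer a legitimate question: does ropivacaine add to standard care?

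All of this stands as a limit on size, and the last point means the pain-score analysis should be kept. It does not supply the missing rule. The primary hypothesis concerns movement pain alone, and being able to see lower rescue use in a secondary table is not a prespecified joint reading.

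**Conclusion.** The concern holds as attenuation. A shared, score-targeted ladder pulls the movement-pain contrast toward no difference if ropivacaine works, and neither the analysis nor the sample size allows for it. With half of the triggered women rescued, power falls from about 79% to about 45% (movement trigger) or about 72% (rest trigger). These figures rest on an assumed control mean of 50 mm, SD of 22 mm, a 40% reduction before rescue, 3 read as 30 mm, rest pain at half of movement pain, and a single t-test; none is a figure from the documents except the 40% and the 20 per arm. The direction is firm and the size is not. A null on pain scores alone would be ambiguous, and the plan should say in advance how it will be read.

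**What to change.** The rescue rules stay as they are.

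1. **Timing.** Where a scheduled pain score and a rescue request coincide, record the score first. For every scheduled score, record the drug and time of the last rescue, or derive them from the nursing and pharmacy records already being abstracted. The second part is needed because rescue is largely as needed, so a dose may fall shortly before a score. The protocol should also say which score, rest or movement, the ladder refers to.
2. **Joint analysis.** Beside the pain-score analysis, prespecify one integrated rank score per woman. Rank all women on a prespecified movement-pain summary and on cumulative rescue use, express each as a percentage difference from the mean rank, and add them. Compare each ropivacaine arm with saline. Rescue use must cover NSAIDs as well as morphine equivalents, because ketorolac is always the first rescue drug and ibuprofen follows later; a score using opioid alone would miss women rescued by NSAID only. State how the two NSAIDs are combined before ranking: in raw milligrams one 600 mg ibuprofen dose weighs as much as 600/30 = 20 ketorolac doses, so separate ranks or dose counts are safer.
3. **Reporting rule.** State that similar pain scores with lower rescue use will not be reported as no analgesic effect.

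The cost is small: one added analysis from outcomes already planned, and at most a line on the scoring sheet (the data collection instrument is not in the text supplied and may already have it). The downside is that the integrated score is in rank units and harder to read clinically, so pain scores, opioid mg and NSAID mg should still be shown separately. The change is credible only if made before unblinding.

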# **Participant Selection**

The study will take place at Emory University Hospital Midtown (EUHM), which cares for a mixed community- and university-based obstetric practice. Parturients will be recruited from the patient pools of both private and Emory physicians, and enrolled after appropriate consent has been obtained. The inclusion criteria for the study includes all ASA class I-III parturients at least 34 weeks pregnant, that are 18 years or older, have never had a cesarean section, have had one or two prior cesarean sections, and are undergoing scheduled or unscheduled non-emergent cesarean sections with spinal anesthesia. Exclusion criteria includes parturients who have allergies to morphine, ketorolac, or amide local anesthetics; pregnancies less than 34wks gestational age; significant maternal cardiac, liver, or renal disease; maternal history of narcotic abuse or dependency; presence of a pre-operative fever ( $\geq 100.4$  °F); emergent cesarean sections with or with-out general anesthesia; and patients in whom valid consent is questionable (non-English speakers or mentally-impaired individuals). Study patients have the option of withdrawing from the study at any point, as the On-Q® pump infusion can be simply discontinued and the catheter removed. At such time the patient would revert to our standard pain management protocol.

# **Statistical Analysis**

Based on a preliminary sample size calculation using an  $\alpha$  risk of 0.05, a  $\beta$  risk of 0.2, and an effect size involving a 40% reduction in pain scores, we estimate that 20 patients are needed in each arm of the study. Data normality will be tested using the Kolmorgorov-Smirnov test. Normally distributed data will be presented as means  $\pm$  SD, whereas non-normally distributed data will be expressed as medians with interquartile ranges. Categorical data will be reported as frequencies. VAS scores will be analyzed using two-way ANOVA for repeated measures. Non-normal data will be analyzed using the Friedman test. Categorical data will be analyzed using the X test. Multiple comparisons will use a Bonferroni correction. Differences will be considered statistically significant at a P<0.05.

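### A Kolmogorov-Smirnov result chooses the summary and test for continuous outcomes, but it is miscalibrated in standard form and weak for moderate skew at 20 per arm

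*Combined protocol and SAP*

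**What the plan says.** The rule is in the Statistical Analysis section of the combined protocol and SAP. It opens with "Data normality will be tested using the Kolmorgorov-Smirnov test". Two consequences follow for the summary: "Normally distributed data will be presented as means" with SD, whereas "non-normally distributed data will be expressed as medians with interquartile ranges". One follows for the test: "Non-normal data will be analyzed using the Friedman test". Pain scores also have a named method: "VAS scores will be analyzed using two-way ANOVA for repeated measures". The plan does not say whether a VAS score found non-normal stays with that ANOVA or moves to Friedman. It names no test for other continuous outcomes that pass as normal.

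The section does not say whether normality is checked per arm, pooled or on residuals, at which time points, at what level, or with any correction for an estimated mean and SD. The only threshold given is general: "Differences will be considered statistically significant at a P<0.05".

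The Objectives section lists the outcomes exposed to this rule: pain on a 100 mm line, opioid use in mg of morphine equivalents by day and in total, and NSAID use in mg. All are bounded at zero.

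**The concern.** The tabulated Kolmogorov-Smirnov (K-S) p-value is valid only if the reference mean and SD are known beforehand. The plan supplies neither, so both must come from the women being tested. The fitted curve then lies closer to the data than the table allows for, and the test rejects too rarely.

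Rescue drugs are given as needed, and Study Design and Methodology reserves first-day IV morphine for pain that persists after ketorolac. Zero opioid amounts and right skew are therefore plausible. If such data pass as normal, the reader sees a mean and SD that describe the typical woman poorly. If the verdict varies from sample to sample, the choice of test is made after the data are seen.

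**Working it through.** **The plan's own figure.** The section says "we estimate that 20 patients are needed in each arm of the study", from alpha 0.05, a beta "risk of 0.2, and an effect size involving a 40% reduction in pain scores". No mean or SD is given, so 20 can only be back-solved. With n = 20, two-sided alpha 0.05 and 80% power, the standardised difference is d = √(2/20) × (1.960 + 0.842) = 0.886. A 40% reduction then implies SD = 0.40/0.886 = 0.45 of the control mean. This says nothing about the shape of the data. The documents state no power for the normality test.

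**Inputs.** From the documents: n = 20 per arm, or 60 pooled. Assumed: a 5% level for the normality test, and every shape below. The 30% share of zeros is motivated only by the remark in Introduction and Background that over 70% of patients on neuraxial opioids ask for more analgesia.

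**Method.** D = max over i of {i/n − F(x_i), F(x_i) − (i−1)/n}, with the x_i sorted and F the normal curve at the sample mean and SD. Reject if D exceeds:
- the standard K-S value: 0.294 at n = 20, 0.172 at n = 60;
- the Lilliefors value: 0.192 at n = 20, 0.114 at n = 60.

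There were 20,000 samples per shape (4,000 for Shapiro-Wilk).

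**Percentage of samples declared non-normal**

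| Assumed shape | K-S standard, n=20 | K-S Lilliefors, n=20 | Shapiro-Wilk, n=20 | K-S standard, n=60 | K-S Lilliefors, n=60 |
|---|---|---|---|---|---|
| Normal | 0.0 | 5.2 | 5.9 | 0.0 | 4.8 |
| Gamma, shape 4 (skew 1.0) | 0.2 | 18.4 | 29.4 | 2.6 | 46.9 |
| Gamma, shape 2 (skew 1.4) | 0.8 | 32.3 | 53.5 | 12.8 | 78.0 |
| Exponential (skew 2) | 3.9 | 58.7 | 83.6 | 52.7 | 98.7 |
| Lognormal, sigma 1 | 19.6 | 79.3 | 93.1 | 90.1 | 99.9 |
| VAS: N(20, 20) floored at 0 | 0.1 | 13.4 | 35.3 | 1.0 | 50.2 |
| 30% zeros + gamma (shape 2) | 2.6 | 50.9 | 84.3 | 54.5 | 99.2 |
| 50% zeros + exponential | 54.0 | 98.6 | 99.9 | 100 | 100 |

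A repeat run agreed within about two points: gamma (shape 2) to exponential gave 1 to 4%, 31 to 57% and 52 to 84% in the three n = 20 columns.

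**Stability of the verdict, if tested per arm.** When all three arms share one shape and each is flagged with probability p, the chance that their verdicts differ is 1 − p³ − (1−p)³. With Lilliefors:
- gamma (shape 2): 1 − 0.034 − 0.310 = 66%;
- exponential: 1 − 0.202 − 0.070 = 73%;
- 30% zeros: 1 − 0.132 − 0.118 = 75%.

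Uncorrected, the same formula gives 2%, 11% and 8%. So the standard test passes nearly everything of this kind, while the corrected test often splits the arms. The plan has no rule for a split.

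**Effect on inference.** Three-arm ANOVA at 20 per arm kept its type I error at 3.8 to 5.4% under skewed and zero-inflated shapes. Power moved both ways: for lognormal totals in the ratio 20/12/8, ANOVA had 50% and a rank test 69%; in an exponential scenario, 66% and 57%.

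**The case against.** A reader might infer that the test cannot detect skew at 20 per arm, so that clearly skewed data will pass. The documents do not support that. The statement needs an uncorrected test run per arm, and the plan specifies neither. With Lilliefors the test flags 59 to 79% of strongly skewed samples (exponential to lognormal with sigma 1). With about half zeros, even the standard test flags 54%. A sample of ten zeros and ten values between 5 and 30 mg can be built that just passes (p = 0.051), but the standard test rejects about 77% of samples of that kind. Nor can it be said that early pain scores will usually be called normal: many exact zeros are plausible under a working spinal, and those are what the test finds best.

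A reader might also infer a false-positive problem or harm to the primary analysis. Neither is shown. ANOVA type I error stayed near 5%. VAS scores have a named ANOVA, and a gate that seldom rejects leaves them there.

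These limits stand, but they do not remove the defect. The plan makes the pre-test the rule, and without the missing specification the rule cannot be applied reproducibly. Pooling does not rescue the standard test: at n = 60 it still misses 87% of gamma (shape 2) samples, and pooled raw data mix arm differences into a check that belongs on residuals. Whether Friedman can compare independent arms is a separate matter, not relied on here.

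**Conclusion.** The concern holds in limited form. Run in its standard form with estimated mean and SD, the test is miscalibrated: about 0% rejection of normal data against a nominal 5%. That follows without any assumption about this trial's outcomes. At 20 per arm its power for moderate skew is very low uncorrected and modest when corrected, and below Shapiro-Wilk in both cases. These power figures rest on assumed shapes, because the documents give no skewness or share of zeros, and on per-arm testing, which they do not state.

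What is at stake is the description of zero-bounded secondary outcomes, chiefly opioid and NSAID amounts, and a choice of test that depends on the data. The validity of the primary comparison is not shown to be at risk. A more powerful normality test would reduce the problem but not end it: Shapiro-Wilk still misses about 46% of gamma (shape 2) samples at n = 20. Only a choice made in advance removes the dependence.

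**What to change.** Delete the normality gate and fix the summary and test by outcome:

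- **VAS scores:** the planned repeated-measures model whatever their shape, with residual plots as a check.
- **Opioid and NSAID amounts, and satisfaction:** median (IQR) with a between-arm rank test (Kruskal-Wallis), then Bonferroni-corrected pairwise comparisons with control.
- **Times to first rescue drug and to first opioid:** Kaplan-Meier curves and a log-rank test.
- **Any normality check retained:** on model residuals, for information only, with no effect on the analysis.

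The cost is a few sentences in the Statistical Analysis section, with no added patients or data. The downside is small: for some skewed shapes the rank test has somewhat less power than ANOVA (57% against 66% in the exponential scenario above), while for others it has more.
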